7.4. ADVERSE EVENTS REQUIRING EXPEDITED REPORTING

The Investigator will report all SAEs and device deficiencies that could have led to a SADE; this information shall be promptly followed by detailed written reports [EN ISO 14155:2012 § 9.8 b].

The Investigator will document all SAEs and SADEs, including device deficiencies in the study subject's file and report it to the Sponsor and to the Clinical Research Organization (CRO) within 24 hours of knowledge of event. When medical reports (lab results, examinations, etc.) associated with AEs are submitted to the Sponsor or CRO, all personal subject information (name, address, etc.) *must* be removed or redacted. The redacted materials must be identified only with the subject ID number.

Upon notification of SAEs, the Sponsor will initiate and complete a review and evaluation of the event within time frames that will maintain reporting compliance with applicable regulatory agencies. The Sponsor is responsible for classification and reporting of AEs and ongoing safety evaluation of the clinical investigation in line with EN ISO 14155:2012 and regulatory requirements. If insufficient information is available to reach a definitive diagnosis, the Sponsor may instruct the monitor responsible for the site to contact the site to request additional confirmatory information, if any.

In the event of a subject's death, the Investigator will make reasonable effort to obtain a copy of the autopsy report and/or death summary. The Investigator will determine the cause of death and its relationship to the investigational device; the Investigator will record results on the AE case report form (CRF). The Investigator will include copies of an autopsy report, if available, and/or a death summary with this form.

The Investigator is responsible for reporting all SAEs, SADEs, and device deficiencies that could have led to a SADE to the EC, according to national regulations and EC requirements. The investigator will forward a copy of this report to the Sponsor and file it in the site regulatory binder.

The Sponsor will ensure that its Authorized Representative will report all SAEs and device deficiencies that could have led to an SADE to the Competent Authorities in accordance with European Medical Devices directives and all applicable national regulations.

7.5. ANTICIPATED ADVERSE EVENTS

Anticipated complications/AEs are defined as complications/events that can be reasonably associated with catheter ablation procedures.

Anticipated AEs include, but are not limited to:

- Air embolism
- Allergic reaction (including anaphylaxis)
- Anesthesia reaction
- Angina
- Aorto-right atrial fistula
- Arrhythmias, including exacerbation of pre-existing atrial fibrillation
- Arterial-venous fistula
- Cardiac perforation/ tamponade
- Cardiac thromboembolism
- Cardiac or respiratory arrest
- Catheter entrapment

- Cerebrovascular incident / Stroke
- Chest pain/discomfort
- Congestive heart failure
- Coronary artery dissection
- Coronary artery spasm
- Coronary artery thrombosis / occlusion
- Death
- Diaphragmatic paralysis
- Dislodgement of ICD or permanent pacing leads
- Endocarditis
- Esophageal ulceration
- Gastroparesis
- Heart failure / pump failure
- Hemoptysis
- Hemoptysis
- Hemothorax
- Hypotension
- Hospitalization (initial and prolonged)
- Increased creatinine phosphokinase (CPK) level
- Infections
- Laceration
- Leakage of air or blood into the lungs or other organs due to perforation
- Left atrial esophageal fistula
- Major bleeding, requiring surgery or transfusion
- Myocardial infarction
- Obstruction or perforation or damage to the vascular system
- Pericarditis
- Pericardial effusion
- Phrenic nerve damage including Diaphragmatic paralysis
- Pleural effusion
- Pneumonia
- Pneumothorax
- Pulmonary edema
- Pulmonary embolism
- Pulmonary vein dissection
- Pulmonary vein thrombus
- Pulmonary hypertension
- Respiratory depression
- Skin burns
- Severe PV stenosis or complete occlusion, even asymptomatic
- Tamponade, potentially requiring surgery
- Temperature elevation or fever
- Transient Ischemic Attack (TIA)
- Thromboembolism

- Thrombosis
- Unintended complete or incomplete AV, Sinus node, or other heart block or damage
- Valve damage
- Vascular bleeding / local hematomas / ecchymosis
- Vasovagal reactions
- Ventricular tachyarrhythmia
- Volume overload

7.6. **DEVICE DEFICIENCIES**

Device deficiency is defined as an inadequacy of a medical device with respect to its identity, quality, durability, reliability, safety or performance.

Note, device deficiencies include malfunctions, use errors, and inadequate labelling. All device deficiencies or malfunctions that occur during the course of the trial and could have led to an SAE must be reported, whether or not they were associated with an AE.

Device malfunction: failure of an investigational medical device to perform in accordance with its intended purpose when used in accordance with the instructions for use.

User error: act or omission of an act that results in a different medical device response than intended by the manufacturer or expected by the user.

The Device Deficiency CRF is specific for reporting all device deficiencies, or malfunctions that occur during the course of the trial, whether or not they were associated with an adverse event. Device Deficiency CRFs should be submitted to the Sponsor and CRO within 24 hours of the occurrence defining the device deficiency.

Anticipated device deficiencies and malfunctions include but are not limited to:

- Catheter deflection deficiency or failure
- Malfunction of a catheter electrode
- Malfunction of a catheter temperature sensor
- Unexpected termination of ablation due to internal system error
- Failure to initiate ablation due to internal system error
- Temporary or sustained loss of catheter navigation/visualization capability

8. STATISTICAL METHODS

8.1. SAMPLE SIZE CALCULATION

This trial is intended to demonstrate safety and performance of the device and system. As a result, no formal statistical hypothesis was applied to derive to the sample size.

8.2. STUDY OUTCOMES

8.2.1. SAFETY

The primary safety outcome is the rate of the following SAEs occurring starting Day 0 and extending through the Day 10 follow-up visit:

- TIA
- CVA
- Major bleeding
- Cardiac tamponade
- Pulmonary vein stenosis
- Severe pericarditis requiring hospitalization
- Myocardial infarction
- Diaphragmatic paralysis
- Atrio-esophageal fistula (through the Day 90 assessment)
- Valvular damage
- Phrenic nerve palsy
- Intra-procedural device complications requiring open chest or heart surgery
- Vascular complications requiring surgical intervention
- Death

8.2.2. DEVICE PERFORMANCE

The primary product performance outcome is determined during the procedure, and is defined as the following:

- Catheter handling sufficient to reach reasonable intended targets, as determined by the physician:
 - catheter delivery to the desired cardiac chambers
 - manipulation of catheter
 - completion of mapping procedure
 - o safe removal of catheter from the subject
- 3D electro-anatomical map creation and utility sufficient to aid diagnosis
- Generation of acceptable acute therapeutic RF lesions

The secondary product performance outcome is freedom from documented recurrence of the treated arrhythmia detected by ambulatory monitoring at the Day 90, Day 180, and Day 365 Visits. In AF subjects, this includes freedom from documented recurrence of AF, AT, or AFL. Recurrence is defined as any episode lasting longer than 30 seconds.

8.3. **Descriptive Analyses**

Continuous variables will be summarized using standard quantitative statistics: number of non-missing observations, mean, standard deviation, median, quartiles and range (minimum and maximum observed values). The number of missing observations, if any, will also be summarized.

Categorical variables will be summarized using classical frequency statistics: number of non-missing observations and percentages by categories. Number and percent of missing data, if any, will also be summarized.

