5.4.4. VISIT 2: DAY 0 – INDEX ABLATION PROCEDURE

After documenting concomitant use of AADs and other important cardiovascular medications and confirming the absence of atrial thrombus or another abnormality precluding catheter introduction, catheters are introduced percutaneously and advanced to the chamber of interest. For left atrial procedures, if the esophagus is not mechanically deviated away from the left atrium, a temperature probe may be placed in the esophagus to monitor heating during the procedure.

The heart chamber is mapped using the Affera Sphere-9 Ablation Catheter and the Affera Mapping System to generate a representation of the heart and to locate the areas of the heart that are creating or propagating problematic electrical signals that interfere with the proper rhythm. In addition, pacing is used to identify the location of the phrenic nerve.

Ablation using the Affera Sphere-9 Ablation Catheter and the Affera RF Generator is performed, and data regarding ablation delivery is recorded by the Affera Mapping System. Procedural success is monitored by mapping and/or pacing to verify termination and non-inducibility of the arrhythmia (all subjects) and/or successful isolation of target pulmonary veins. Any serious procedural adverse events (AEs) will be documented.

Prior to discharge, the following will be documented:

- Vital signs
- 12-lead EKG
- Serious adverse events (AEs)

At the discretion of the investigator, the following assessments can be performed prior to discharge:

- Transthoracic echocardiography (TTE)
- Endoscopic evaluation of the esophagus
- CT or MR imaging

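### The target-reaching part of catheter handling is scored by the physician against targets that need not be recorded beforehand, so the descriptive handling rate can be biased upward

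*Combined protocol and SAP*

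**What the plan says.** Section 8.2.2 begins: "The primary product performance outcome is determined during the procedure, and is defined as the following". The first component is "Catheter handling sufficient to reach reasonable intended targets, as determined by the physician". That line ends in a colon and is followed by four sub-items: "catheter delivery to the desired cardiac chambers", "manipulation of catheter", "completion of mapping procedure" and "safe removal of catheter from the subject". Two further components follow: a 3D map good enough to help diagnosis, and "Generation of acceptable acute therapeutic RF lesions". The synopsis repeats the same structure, and section 5.2 gives it in shortened form.

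The procedure itself is in section 5.4.4. On where the catheter should go, it says that "catheters are introduced percutaneously and advanced to the chamber of interest", and later it refers to the pulmonary veins being targeted. It also says that mapping with the Sphere-9 is used to find the areas responsible for the arrhythmia. The schedule in Appendix 1 has no item for planned targets.

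Section 8.1 states that no formal hypothesis underlies the sample size, which is at most 30 subjects in one arm at one center (section 5.2). Section 8.3 summarizes categorical outcomes by counts and percentages, and the synopsis makes the subject the unit.

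**The concern.** Three judgements decide whether the target-reaching part succeeds: which targets were intended, which of those were reasonable, and whether handling was sufficient to reach them. Section 8.2.2 leaves all three to the physician and defines none of them. Because no list has to exist before the attempt, the set of targets that counts can shrink after an attempt has failed. A site that was planned and not reached can be set aside as unreasonable, and the subject is still scored as a success on this part.

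The trial has no control arm, no hypothesis and no threshold, so the reported percentage is itself the evidence on handling. Section 1.1 names handling among the features on which the expectation of safe and effective treatment rests. If the denominator can move with the result, the percentage shows that the physician was satisfied. It does not show that the catheter reached what was planned.

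**Working it through.** The plan gives no expected rate, threshold or power, so there is no figure of its own to reproduce. The check is first one of text, then an illustration of size.

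**Text**

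| Question | What the document gives |
|---|---|
| Which targets? | 8.2.2: those the physician regards as reasonable and intended; no definition |
| Recorded beforehand? | 5.4.4 and Appendix 1: no requirement |
| How is a missed target scored? | No rule |
| Who scores? | 8.2.2: the physician; no independent assessor |
| When? | 8.2.2: during the procedure |
| What can fail whatever the targets? | 8.2.2: mapping completion, safe removal, map utility, lesions |

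Two of the four sub-items (mapping completion and safe removal) are close to checkable facts. The other two (delivery to the desired chambers, manipulation) carry no criterion and stay open to the same judgement.

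**Size (illustration only)**

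Inputs: n = 30, the maximum in section 5.2, assuming full enrollment. Let q be the true share of subjects with at least one missed target, assumed 10% with a range of 5% to 20%. Let h be the share of those misses that are set aside, which is unknown and therefore run from 0 to 1. The unit is the subject, and subjects are taken as independent.

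Expected recorded misses = n × q × (1 − h). Chance of a perfect report = (1 − q(1 − h))^30.

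At q = 10%:

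| h | Recorded misses expected | Chance of 30/30 |
|---|---|---|
| 0 | 30 × 0.10 = 3.0 | 0.90^30 = 4.2% |
| 0.5 | 30 × 0.05 = 1.5 | 0.95^30 = 21.5% |
| 0.8 | 30 × 0.02 = 0.6 | 0.98^30 = 54.5% |
| 1 | 0 | 100% |

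With three subjects missing a target, the report is 27/30 (90%) if no miss is dropped and 30/30 (100%) if all are. The exact (Clopper-Pearson) 95% lower limits are 73.5% and 88.4%.

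At q = 20%, the expected result with none dropped is 30 × 0.8 = 24, that is 24/30 (80%, lower limit 61.4%), against at most 30/30. At q = 5%, 30 × 0.05 = 1.5 misses are expected. The chance of 30/30 is then 21.5% with none dropped, 46.8% with half dropped and 74.0% with 80% dropped.

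**The case against.** The strongest reply is that the handling criterion does not end at the colon. The four sub-items give it content. A map not completed or a catheter not safely removed is a failure under any list of targets, and the map and lesion components can fail independently. This stands. A reader might infer that the primary performance outcome can hardly fail, and the text does not support that. Only the target-reaching judgement is loose in the way described here.

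Second, section 8.2.2 fixes the outcome during the procedure. A reader might infer that targets could be rewritten afterwards, but the plan does not describe that. Re-judging after a failed attempt within the same procedure does remain possible.

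Third, 8.2.2 says the physician and does not say the operator. That they are the same person is likely at a single center, but it is an inference. What the text does show is that nobody independent is required.

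Fourth, a reader might take handling to be the part of the outcome most specific to this new catheter. Section 2.1 points the other way: it describes the steering mechanism and shaft materials as similar to marketed catheters, and the expandable electrode as the unique feature.

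Fifth, there are partial cross-checks. Section 5.4.4 has procedural success verified by mapping and/or pacing and has ablation data stored by the mapping system. Section 7.6 requires device deficiencies, with deflection failure listed among them, to be reported within 24 hours. These leave a record of many catheter-related failures, but nothing feeds them into the handling outcome. The CRFs are not part of the document, so a target field may exist there. Even then, 8.2.2 has no rule that uses it.

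Finally, a list made before insertion cannot contain sites found only by mapping. That is a fair constraint on any remedy.

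**Conclusion.** The point holds for the target-reaching part of catheter handling. The yardstick is discretionary, nothing fixes it before the attempt, and the error can run in only one direction: a missed target can be removed, which raises the reported rate.

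The size cannot be determined from the document. Under the assumed 10% of subjects with a missed target and n = 30, the reported rate lies between 27/30 and 30/30, depending entirely on how many misses are set aside. The upper end requires that every one is dropped, which is the extreme case and not a prediction.

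Since there is no hypothesis or threshold, no formal study decision turns on the difference. The consequence is a descriptive percentage that is hard to interpret and may be too favorable. The change is worth making before procedures begin, because prior intent cannot be reconstructed reliably later.

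**What to change.** **Section 5.4.4 and the CRF.** Before the Sphere-9 is introduced, record the intended chambers and anatomical targets for that subject. Record any target added from the map before ablation at it is attempted.

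**Section 8.2.2 (and the synopsis).**
- Score each recorded target as reached or not reached with the Sphere-9.
- Keep every recorded target in the denominator unless a documented reason unrelated to the catheter applies, for example that the map showed a different mechanism.
- List all such exclusions, and report the rate a second time with them counted as not reached. The reader can then see how much rests on the exclusions, which are themselves a judgement.
- Keep the four existing sub-items and report each separately.
- Keep the physician's overall rating as supportive information.

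**Cost.** One CRF entry per procedure and a few sentences in the protocol. There is no added procedure for the subject and no change to treatment. The reported success rate may be lower than under the current wording.

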	After confirmation of the absence of left atrial thrombus precluding catheter introduction, eligible subjects will undergo mapping and ablation. Esophageal evaluation, and CT and/or MR imaging may optionally be performed after treatment or during follow-up.
	Subjects will be followed for 365 days after the ablation procedure to characterize safety and product performance. Note, the Day 10 visit can be conducted by telephone. Ambulatory monitoring will be conducted within the follow-up windows at Day 90, Day 180 and Day 365. Use of antiarrhythmic drugs (AADs) and other important cardiovascular drugs will be collected at every visit. Serious adverse events (AEs) will be collected starting on Day 0 through study exit.
SCHEDULE OF Examinations	Visit 1 - Screening (within 30 days) Visit 2 - Ablation (Day 0) Visit 3 - Day 10 ± 3 days (telephone call) Visit 4 - Day 90 ± 14 days Visit 5 - Day 180 ± 30 days Visit 6 - Day 365 ± 30 days
Study Outcomes	Safety: The primary safety outcome is the rate of the following serious adverse events (SAEs) occurring starting Day 0 and extending through the Day 10 assessment: transient ischemic attack; cerebrovascular accident; major bleeding; cardiac tamponade; pulmonary vein stenosis; severe pericarditis requiring extended hospitalization; myocardial infarction; diaphragmatic paralysis; atrio-esophageal fistula (through the Day 90 assessment); valvular damage; phrenic nerve palsy; intra-procedural device complications requiring surgical intervention; and death.
	 Device performance: The primary product performance outcome is determined during the procedure and is defined as the following: Catheter handling sufficient to reach reasonable intended targets, as determined by the physician: catheter delivery to the desired cardiac chambers manipulation of catheter

	 completion of mapping procedure safe removal of catheter from the subject 3D electro-anatomical map creation and utility sufficient to aid diagnosis Generation of acceptable acute therapeutic RF lesions
	The secondary product performance outcome is freedom from documented recurrence of the treated arrhythmia through the Day 365 post-treatment follow-up visit. In AF subjects, this includes freedom from documented AF, atrial tachycardia (AT), or AFL.

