5.2. STUDY DESIGN

This is a prospective, single-arm, single center study involving the Affera Sphere-9 Ablation Catheter and the Affera Mapping and Ablation System in up to 30 patients. The arrhythmias treated in this study are common atrial arrhythmias: atrial flutter (AFL), paroxysmal atrial fibrillation (AF), and persistent atrial fibrillation.

The primary safety outcome is the rate of the following serious adverse events (SAEs) occurring starting Day 0 and extending through the Day 10 assessment:

transient ischemic attack; cerebrovascular accident; major bleeding; cardiac tamponade; pulmonary vein stenosis; severe pericarditis requiring extended hospitalization; myocardial infarction; diaphragmatic paralysis; atrio-esophageal fistula (through the Day 90 assessment); valvular damage; phrenic nerve palsy; intraprocedural device complications requiring open chest or heart surgery; vascular complications requiring surgical intervention; and death.

The primary product performance outcome is determined during the procedure and includes catheter handling, 3D electro-anatomical map creation and utility sufficient to aid diagnosis, and generation of acceptable acute therapeutic RF lesions.

The secondary product performance outcome is freedom from the treated arrhythmia detected by ambulatory monitoring or ICD interrogation at the Day 90, Day 180, and Day 365 Visits. In AF subjects, this includes freedom from documented AF, AT, or AFL.

Pre-screening, i.e., medical record review without obtaining informed consent, is allowed.

Initial Screening Activities. After providing informed consent, initial screening consisting of review of relevant history including duration and frequency of arrhythmia(s), their subsequent treatments (e.g., medications, previous ablation) and associated symptoms will be performed.

If the subject passes the initial screening, remaining screening tests will be performed which include assessment of study eligibility, demographics, concomitant use of antiarrhythmic drugs (AADs) and other important cardiovascular drugs, physical exam, vital signs, 12 lead EKG, hematology, transthoracic echocardiography (TTE), urine pregnancy test (women of childbearing potential only), and optional CT and/or MR imaging

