After confirmation of the absence of atrial thrombus precluding catheter introduction, eligible subjects will undergo mapping and ablation. Subjects will be assessed for potential adverse events prior to discharge. Esophageal evaluation, and CT and/or MR imaging may optionally be performed after treatment or during follow-up.

Subjects will be followed for approximately 365 days after the ablation procedure to characterize safety and product performance. Note, the Day 10 visit can be conducted by telephone. Ambulatory monitoring for a minimum of 48 hours will be conducted within the follow-up windows at Day 90, Day 180, and Day 365. Use of antiarrhythmic drugs and other important cardiovascular drugs will be collected at every visit. Serious adverse events (AEs) will be collected starting on Day 0 through study exit.

A summary of the schedules of evaluations and visits can be found in Appendix 1.

5.3. Subject Population

Up to a total of 30 subjects meeting the following study entry criteria will be treated.

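### The one-year freedom outcome is cumulative in the Synopsis but tied to three visits in Sections 5.2 and 8.2.2, and no rule says that an early recurrence stays a failure or stays in the denominator

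*Combined protocol and SAP*

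**What the plan says.** The secondary performance outcome is defined three times.

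- **Synopsis, Study Outcomes:** "freedom from documented recurrence of the treated arrhythmia through the Day 365 post-treatment follow-up visit". This is cumulative.
- **Section 5.2:** "freedom from the treated arrhythmia detected by ambulatory monitoring or ICD interrogation at the Day 90, Day 180, and Day 365 Visits".
- **Section 8.2.2:** "freedom from documented recurrence of the treated arrhythmia detected by ambulatory monitoring at the Day 90, Day 180, and Day 365 Visits". It adds: "Recurrence is defined as any episode lasting longer than 30 seconds".

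The only analysis is the generic text of Section 8.3. For categorical variables it gives "number of non-missing observations and percentages by categories", together with the number and percent missing. It does not mention this outcome, a time-to-event method, or any rule for missed visits or early exits.

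Section 5.5.2 lists repeat ablation with a non-study device among the possible reasons for discontinuation. It treats non-attendance before Day 365 as a missed visit and does not say how either case enters the outcome.

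**The concern.** The Synopsis asks whether a subject ever had a documented recurrence up to Day 365. Sections 5.2 and 8.2.2 can be read as asking what each of three recordings showed. These are different quantities, and the plan does not choose between them.

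Under the visit-by-visit reading, a documented early failure can disappear from the Day 365 result in two ways:

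- The subject has a clean recording of at least 48 hours in the Day 365 window and is tabulated as free.
- The subject leaves before Day 365 and has no Day 365 observation. Repeat ablation with a non-study device is a plausible consequence of recurrence, so such exits need not be unrelated to the outcome.

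This is the study's only defined long-term performance outcome. With the definition left open, the choice between the readings could be made after the data are seen. The issue is separate from which detection method counts (only Section 5.2 names ICD interrogation), and it would remain once that is settled.

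**Working it through.** The plan states no expected freedom rate, target or power for this outcome, so there is no figure of its own to reproduce. Section 8.1 says that "no formal statistical hypothesis was applied to derive to the sample size". The check compares the two readings by direct counting.

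**Input from the documents.** N = 30, the maximum in Section 5.3: "Up to a total of 30 subjects meeting the following study entry criteria will be treated".

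**Assumed inputs** (none is given in the documents):

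- F = subjects with a documented recurrence at Day 90 or Day 180
- L = subjects whose first recurrence is at Day 365
- c = those of the F who are clean at Day 365
- d = those of the F with no Day 365 data

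All subjects outside F are taken to have Day 365 data.

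**Formulas**

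- Cumulative freedom, all treated subjects: A = (N − F − L) / N
- Day 365 visit figure, subjects with Day 365 data: B = (N − F − L + c) / (N − d)

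Raising c increases the numerator of B and raising d reduces its denominator. B is therefore never below A, and the two are equal when c = d = 0, that is, when every early failure is monitored and still recurrent at Day 365.

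**Main illustration, F = 6, L = 3.** A = (30 − 6 − 3)/30 = 21/30 = 70.0% (exact 95% interval 50.6 to 85.3).

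| c | d | B | B − A (points) |
|---|---|---|---|
| 0 | 0 | 21/30 = 70.0% | 0.0 |
| 0 | 2 | 21/28 = 75.0% | 5.0 |
| 2 | 0 | 23/30 = 76.7% | 6.7 |
| 2 | 2 | 23/28 = 82.1% | 12.1 |
| 0 | 6 | 21/24 = 87.5% | 17.5 |
| 6 | 0 | 27/30 = 90.0% | 20.0 |

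**Other assumed failure counts, with one third of early failures clean and one third without data**

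| F | L | A | B | B − A (points) |
|---|---|---|---|---|
| 3 | 1 | 26/30 = 86.7% | 27/29 = 93.1% | 6.4 |
| 9 | 3 | 18/30 = 60.0% | 21/27 = 77.8% | 17.8 |
| 12 | 4 | 14/30 = 46.7% | 18/26 = 69.2% | 22.6 |

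**Subjects with no recurrence but incomplete monitoring.** The cumulative reading needs a rule here too. Take F = 6 and L = 3, and suppose m of the 21 recurrence-free subjects lack Day 365 data. Counting them as failures gives (21 − m)/30, and counting them as free gives 21/30 = 70.0%. For m = 2 the range is 63.3% to 70.0%; for m = 4 it is 56.7% to 70.0%.

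**The case against.** The strongest reply is that Section 8.2.2 defines one outcome, not three. It names the three visits jointly and counts any episode over 30 seconds. *At* may only say when monitoring takes place, since recordings are scheduled only in those windows. On that composite reading a Day 90 recurrence stays a failure, its outcome is already known, and the section largely agrees with the Synopsis. This stands as a reasonable reading and would remove the first effect. The text does not select it, however. It also leaves open how to count a subject with no recurrence who is clean at Days 90 and 365 but missed Day 180, and which denominator applies.

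Several stronger inferences are tempting, and the documents do not support them:

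- *The plan has fixed a biased visit-specific analysis.* It has not. It permits one, and the upward bias is conditional on that reading.
- *Section 8.3 makes the non-missing count the denominator.* It lists that count beside the percentages without saying so. It also requires missing data to be reported, so exits would be visible.
- *The Day 365 percentage will be the headline.* No section names it as such.
- *The visit figure spoils a comparison with the recurrence rates in Section 1.* Those are two-year rates of atrial fibrillation or tachycardia. This study follows a mix of flutter and fibrillation for one year, so a cumulative rule would not make them comparable either.

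It is also fair to say that the stakes are limited: the outcome is secondary and descriptive, in a single arm, with no success threshold.

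**Conclusion.** The concern holds as an unresolved conflict of definition. One outcome has two time structures, and no rule combines the visits, makes a recurrence permanent, or keeps a subject who fails and then exits in the denominator. If the visit-by-visit reading is used, early failures that turn clean or exit can only raise the Day 365 figure. In the main illustration the excess runs from 0 to 20.0 points. In the scenarios with one third clean and one third without data it is 6.4 to 22.6 points.

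These sizes rest entirely on assumed counts; the direction does not. The excess is zero if every early failure is recorded as still recurrent at Day 365. Because no decision rule depends on the outcome, this should be corrected but does not threaten the study's design.

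**What to change.** Use one cumulative definition, following the Synopsis, in the Synopsis and in Sections 5.2 and 8.2.2. Suggested wording: *A subject with any documented recurrence (longer than 30 seconds) at any time from the ablation through the Day 365 visit, window included, is a failure and remains a failure, including after missed visits or exit.*

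In Section 8.3:

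- Report as the headline the proportion free among all treated subjects.
- State how subjects with no recurrence and an incomplete set of recordings are counted, for example as a range with all of them failures and all of them free.
- Label visit-by-visit percentages as supportive.

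A Kaplan-Meier or interval-censored estimate is optional. Detection occurs mainly at three scheduled recordings, so event times would largely reflect visit dates. The final window is also ±30 days: a clean last recording on Day 340 would be censored before Day 365, and a recurrence found on Day 380 would fall after it. Any such estimate must therefore treat the whole Day 365 window as one time point.

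The cost is a few sentences and no new data. The downside is that the reported one-year freedom may be lower than a Day 365 visit percentage.
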